### **2.3 Baseline and change from baseline**

In general, the last non-missing observation prior to the first dose of study treatment will serve as the baseline measurement. If there is no value prior to the first dose of study treatment, then the baseline value will not be imputed and will be set to missing.

Unless indicated otherwise, Visit 2 (Week 0) is the planned baseline visit, for all assessments carried out at the center.

Change from baseline will be calculated as the post-baseline assessment value minus the baseline assessment value. If either value is missing, then the change from baseline value will be missing.

### **2.4 Handling of dropouts and missing data**

Unless otherwise specified, missing data will not be imputed. All missing data will be reported to data management to be queried.

## **3. PRIMARY AND SECONDARY VARIABLES**

### **3.1 Primary outcome variables**

Three primary endpoints will be evaluated in this study as follows.

- Proportion of patients/caregivers who successfully administered benralizumab 30 mg SC by injection with an AI at home.

The proportion will be calculated among all patients/caregivers who have been deemed by the Principal Investigator to be suitable for at-home administration and are still in the study at the time of benralizumab injection at Week 12 or Week 16. Patients who are still in the study is defined as patients who had been treated for the specified time point. A successful administration is defined as an injection completed, an answer of “Yes” to all 5 questions in the Questionnaire, and adequately passed the visual inspection and function tests. Patients/caregivers who are unwilling to self-administer at Week 8 will not be considered as

failures, but will be counted as unsuitable for at-home administration and follow the premature IP Discontinuation (IPD) procedure.

- Proportion of returned AI used to administer benralizumab at home that have been evaluated as functional among all returned AI used to administer benralizumab at home.

A functional AI is defined as an answer of “Yes” to all the questions in the visual inspection and function tests. Devices that are not returned for evaluation will be excluded from analysis.

- Proportion of AI used to administer benralizumab at home or in the clinic and have been reported as malfunctioning (Product Complaints).

The first 2 endpoints above will be calculated at Weeks 12 and 16, while the third endpoint will be calculated at Week 0, 4, 8, 12 and 16 as well as for the overall study period (from Week 0 to Week 16), the in-clinic administration period (from Week 0 to Week 8) and the at-home administration period (from Week 12 to Week 16).

In addition, the following variables will be calculated among all patients/caregivers who have been deemed by the Investigator to be suitable for at-home administration at Week 8 and are still in the study at Week 16:

- Proportion of patients/caregivers who successfully administered benralizumab with an AI at both Weeks 12 and 16
- Proportion of patients/caregivers who returned an AI used to administer benralizumab at home and evaluated as functional at both Weeks 12 and 16.

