## **Statistical methods**

The primary endpoints are the proportion of patients/caregivers who successfully administered benralizumab with an AI at home, the proportion of returned AIs used to administer benralizumab at home that have been evaluated as functional, and the proportion of AIs used to administer benralizumab at home or at the clinic and have been reported as malfunctioning (Product Complaints). Additional variables include the proportion of patient/caregivers who successfully administered benralizumab with an AI at both home administrations and the proportion of patients/caregivers who have returned AIs used to administer benralizumab at home that have been evaluated as functional at both times. All these endpoints will be presented using descriptive statistics and exact 95% confidence interval (CI) estimates. The estimated sample size recruitment of 120 patients is based upon a targeted recruitment and successful enrollment of 100 patients plus an adjustment to account for an assumed patient dropout rate of approximately 17% (20 patients); therefore, no hypotheses will be tested statistically and the endpoints and safety results will be summarized descriptively and all data will be listed.

TABLE OF CONTENTS	PAGE
TITLE PAGE.....	1
VERSION HISTORY .....	2
PROTOCOL SYNOPSIS .....	3
TABLE OF CONTENTS .....	7
LIST OF ABBREVIATIONS AND DEFINITION OF TERMS.....	11
1. INTRODUCTION .....	13
1.1 Background .....	13
1.2 Rationale for study design, doses, and control groups.....	14
1.3 Benefit/risk and ethical assessment.....	14
1.4 Study design.....	15
2. STUDY OBJECTIVES.....	17
2.1 Primary objective .....	17
2.2 Secondary objectives .....	17
2.3 Safety objective.....	17
3. SUBJECT SELECTION, ENROLMENT, TREATMENT, RESTRICTIONS, DISCONTINUATION, AND WITHDRAWAL.....	18
3.1 Inclusion criteria .....	18
3.2 Exclusion criteria .....	19
3.3 Subject enrolment and treatment .....	22
3.4 Procedures for handling incorrectly enrolled patients .....	22
3.5 Concomitant medications, restrictions during and after the study.....	23
3.5.1 Concomitant medication .....	23
3.5.2 Restrictions .....	23
3.6 Discontinuation of investigational product.....	25
3.7 Criteria for withdrawal.....	26
3.7.1 Screen failures.....	26
3.7.2 Withdrawal of the informed consent.....	26
3.7.3 Discontinuation of the study .....	26
4. STUDY PLAN AND TIMING OF PROCEDURES.....	27
4.1 Enrollment and screening period .....	30
4.1.1 Enrollment (Visit 1).....	30

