### **3.6 Discontinuation of investigational product**

Patients will be discontinued from IP in the following situations:

1. Patient decision. The patient is free to discontinue treatment at any time without prejudice to further treatment.
2. Adverse event (AE) that, in the opinion of the Investigator, contraindicates further dosing
3. Risk to patient as judged by the Investigator or AstraZeneca
4. Severe non-compliance to study protocol
5. Eligibility requirement found not to be fulfilled (see Section 3.4)
6. Pregnancy
7. Lost to follow-up
8. Development of any study specific criteria for discontinuation:
  1. Anaphylactic reaction to the IP requiring administration of epinephrine
  2. Development of helminth parasitic infestations requiring hospitalization
  3. An asthma-related event requiring mechanical ventilation.
9. A patient who is self-administering IP who becomes unwilling or unable to continue to self-administer must be discontinued. Similarly, if a caregiver is giving the IP and becomes unwilling or unable to continue to administer IP to a patient, then that patient must be discontinued.

All patients who prematurely discontinue IP should return to the study center and complete the procedures described for the Premature IP Discontinuation (IPD) visit after 4 weeks ( $\pm 3$  days) and

---

 Patient is considered lost to follow up when any of the following attempts of contact are failed: -3 attempts of either phone calls, faxes or emails; - having sent 1 registered letter/certified mail; 1 unsuccessful effort to check the vital status of the patient using publicly available sources, if allowed by local regulations.

the procedures for the Follow-up visit after 12 weeks ( $\pm 3$ days) of the last IP administration. The reason(s) for premature discontinuation of IP should be recorded in the eCRF.

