## **3.2 Secondary outcome variable**

### **3.2.1 Asthma Control Questionnaire-6**

The Asthma Control Questionnaire-6 (ACQ-6) is a shortened version of the ACQ that assesses asthma symptoms (nighttime waking, symptoms on waking, activity limitation, shortness of breath, wheezing, and short-acting  $\beta_2$  agonist use) omitting the forced expiratory volume in 1 second (FEV1) measurement from the original ACQ-7 score.

Patients are asked to recall how their asthma has been during the previous week by responding to 1 bronchodilator use question and 5 symptom questions. Questions are weighted equally and scored from 0 (totally controlled) to 6 (severely uncontrolled). The mean ACQ-6 score is the mean of the responses. The mean score will be missing if any symptom score is missing.

The questionnaire will be completed at the study center at Weeks -2, 0, 4, 8, 12, 16, 20 and IPD.

The outcome variable for ACQ-6 will be the change in mean score from baseline (Week 0) to each of the post-treatment periods. There will be no imputation for missing values.

Asthma control responder status will be evaluated as a supportive analysis. Patients will be categorized according to the following limits (Juniper et al 2005), at the end of treatment, where end of treatment is defined as week 20 (EOT visit):

- $ACQ-6 (EOT - baseline) \leq -0.5 \rightarrow$  Improvement
- $-0.5 < ACQ-6 (EOT - baseline) < 0.5 \rightarrow$  No change
- $ACQ-6 (EOT - baseline) \geq 0.5 \rightarrow$  Deterioration

An ACQ-6 responder will be defined as a patient who had improvement on ACQ-6, ie, an ACQ-6 responder variable takes value 1 if change from baseline to end of treatment in  $ACQ-6 \leq -0.5$  and 0 otherwise. Patients with missing or non-evaluable ACQ-6 data at end of treatment visit will be considered non-responders.

Additionally, patients will be categorized according to their ACQ-6 defined asthma control status at the end of treatment using the following score thresholds (Juniper et al 2006):

- $ACQ-6 (EOT) \leq 0.75 \rightarrow$  Well controlled
- $0.75 < ACQ-6(EOT) < 1.5 \rightarrow$  Partly controlled
- $ACQ-6 (EOT) \geq 1.5 \rightarrow$  not well controlled

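### As SAP 3.1 is most naturally read, a patient or caregiver with an observed Week 12 failure who is not dosed at Week 16 drops out of the both-weeks denominators, although the both-weeks result is already known

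*SAP*

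**What the plan says.** SAP 3.1 defines three primary endpoints and then adds two both-weeks variables: successful administration at Weeks 12 and 16, and a returned device evaluated as functional at Weeks 12 and 16. Both are calculated among users "deemed by the Investigator to be suitable for at-home administration at Week 8 and are still in the study at Week 16". The meaning of being still in the study is given earlier in the section, under the first primary endpoint: "Patients who are still in the study is defined as patients who had been treated for the specified time point".

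Protocol 8.4.1.1 uses the same denominator sentence for the two variables but does not define the phrase as having been treated. SAP 6, which lists changes from the protocol, mentions only the physical examination analysis.

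Protocol 3.6 contains a route by which a user may stop after a bad experience at home: "A patient who is self-administering IP who becomes unwilling or unable to continue to self-administer must be discontinued". The same item covers caregivers. Patients who stop investigational product (IP) are asked to return and "complete the procedures described for the Premature IP Discontinuation (IPD) visit after 4 weeks", counted from the last dose, and to attend a follow-up visit 12 weeks after that dose.

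The protocol synopsis names the both-weeks variables together with the primary endpoints and says of the group: "All these endpoints will be presented using descriptive statistics and exact 95% confidence interval (CI) estimates". The denominator therefore affects a reported estimate and its interval.

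**The concern.** Success at both weeks requires success at Week 12. Once a Week 12 home administration has been observed to fail, the both-weeks result is settled: nothing is missing and nothing needs imputing. A denominator that requires a Week 16 dose nevertheless removes that user if IP is stopped in between. No rule in SAP 3.1, or in the general missing-data rule in SAP 2.4, brings the user back.

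The variable is meant to show how often users succeed every time at home. If users who failed and then stopped are left out, the figure can look better than what was observed. It could even exceed the Week 12 success proportion in the same report, which a reader would find hard to understand.

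**Working it through.** **The plan's own figure.** SAP 1.3 treats about 120 patients so that about 100 complete, with 17% drop-out. 100/(1 − 0.17) = 120.5, 120 × 0.83 = 99.6 and 20/120 = 16.7%, so the figure reproduces. The documents give no expected success rate, no count of users dosed at Week 12 and no link between failing and stopping. All counts below are therefore assumptions, with 105 users dosed at Week 12 (between 100 and 120) and everyone dosed at Week 16 also dosed at Week 12.

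**Direction.** Let n be the users dosed at Week 12, X those successful at both weeks, and k the observed Week 12 failures not dosed at Week 16. None of the k can be in X. Keeping them gives X/n; removing them gives X/(n − k). The second is never smaller, and the two are equal only if k = 0 or X = 0. For one removed patient the rise is X/[n(n − 1)]; with X = 97 and n = 105 this is 97/(105 × 104) = 0.9 points.

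**Illustration A (assumed).** 6 of 105 fail at Week 12, 2 others fail at Week 16, and 97 succeed at both. Intervals are exact 95% (Clopper-Pearson). The Week 12 proportion is 99/105 = 94.3% (88.0 to 97.9), whatever happens later.

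| Week 12 failures who stop | Both-weeks proportion | 95% CI |
|---|---|---|
| 0 (or all failures kept) | 97/105 = 92.4% | 85.5 to 96.7 |
| 1 | 97/104 = 93.3% | 86.6 to 97.3 |
| 2 | 97/103 = 94.2% | 87.8 to 97.8 |
| 3 | 97/102 = 95.1% | 88.9 to 98.4 |
| 6 (extreme) | 97/99 = 98.0% | 92.9 to 99.8 |

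The both-weeks figure exceeds the Week 12 figure when 97/(105 − k) > 99/105, that is 105 − k < 102.9, so from k = 3.

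**Illustration B (assumed).** 2 of 105 fail at Week 12 and 1 other at Week 16, so 102 succeed at both. Week 12 is 103/105 = 98.1%. Both-weeks is 102/105 = 97.1%, 102/104 = 98.1% or 102/103 = 99.0% with 0, 1 or 2 stops.

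**When failures are kept.** With S successes and F failures at Week 12, s successes not dosed at Week 16 and b of the remaining successes failing there, the proportion is (S − s − b)/(F + S − s). This cannot exceed S/(F + S), so the both-weeks figure can no longer exceed the Week 12 figure.

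**The two documents.** A patient whose last dose was at Week 12 has the premature-discontinuation visit at Week 12 + 4 = Week 16 and follow-up at Week 12 + 12 = Week 24. That patient can be in the study at Week 16 in the ordinary sense of protocol 8.4.1.1, yet is not treated at Week 16 in the SAP's sense.

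**Cost of keeping failures.** Suppose s users stop for unrelated reasons and failure probability is p per week, independently. The true both-weeks proportion is (1 − p)². Keeping failures but excluding Week 12 successes who leave gives, in expected counts, (105 − s)(1 − p)²/[105 − s(1 − p)].

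- s = 5, p = 0.02: 96.04/100.1 = 95.94% against 96.04%, a tilt of 0.1 points.
- s = 5, p = 0.05: 90.25/100.25 = 90.02% against 90.25%, 0.2 points.
- s = 10, p = 0.10: 76.95/96 = 80.16% against 81.00%, 0.8 points.

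**The case against.** The strongest reply is that the SAP removes everyone not dosed at Week 16, Week 12 successes included. If stopping has nothing to do with the Week 12 result, the planned figure is an unbiased estimate of success at both doses, and keeping only the failures tilts it down. This stands. A reader might infer that the SAP rule always favours success. The documents do not support that: the direction is certain only against the alternative of keeping the known failures, and the true bias depends on a link between failing and stopping that the documents do not quantify.

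The link may also be weak. Users have already injected under supervision at Week 8, and protocol 3.6 does not make a failed injection in itself a reason to stop. Part of the success definition, and the whole of the functional-device definition, comes from the Sponsor's later in vitro evaluation, which the user need not know when stopping. The point is therefore weaker for the functional-at-both variable.

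The failure is not hidden either. It counts in the Week 12 primary proportion, and SAP 4.2.8.1 lists all questionnaire data by patient and visit. No hypothesis is tested.

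Two comparisons are tempting but carry little weight. The synopsis speaks of "the proportion of patient/caregivers who successfully administered benralizumab with an AI at both home administrations" without a Week 16 condition, but it also leaves out the conditions on the first primary endpoint; it is a summary, not a rival denominator. A reader might also infer an inconsistency with the ACQ-6 responder rule, which counts missing end-of-treatment data as non-response. That rule deals with unknown outcomes, whereas here the outcome is known.

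Finally, the treated definition is written under the first primary endpoint. Carrying it over to the both-weeks sentence is an inference, though the same words in the same section make it the natural one.

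**Conclusion.** The point holds in a limited form. If the treated definition carries over, observed Week 12 failures not dosed at Week 16 leave the both-weeks denominators although they are known non-successes. Compared with keeping them, the proportion cannot fall and rises by about 1 percentage point per removed patient at around 100 patients. The rise is zero if no Week 12 failure stops. Its actual size cannot be taken from the documents.

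If the definition does not carry over, protocol 8.4.1.1 may keep the same patient. The denominator is then open to two readings, and SAP 6 records no change. Either way a clarifying sentence is needed.

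A reader might infer that the primary results are inflated. They are not by this route: the Week 12 primary proportion keeps the failure, and the effect is confined to the additional, descriptive both-weeks variables and their exact intervals. A both-weeks figure above the Week 12 figure is possible but needs a large share of failures to stop: 3 of 6 in Illustration A, 2 of 2 in B. This is a cheap improvement worth making, not a threat to the study's main findings.

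**What to change.** In SAP 3.1, and for consistency in protocol 8.4.1.1, state that an observed unsuccessful Week 12 home administration counts as not successful for the success-at-both variable, whatever the Week 16 status. State likewise that a returned Week 12 device evaluated as not functional counts as not functional for the functional-at-both variable.

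Beside this, report how many Week 12 successes were not dosed at Week 16, and give the proportion both excluding them and counting them as not successful. Keep the planned figure, among users dosed at both weeks, as supportive. For example (assumed: 105 dosed at Week 12; 5 fail there, of whom 3 stop; 2 Week 12 successes also stop; 2 others fail at Week 16; 96 succeed at both):

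- failures kept, departing successes excluded: 96/103 = 93.2% (86.5 to 97.2);
- departing successes counted as not successful: 96/105 = 91.4% (84.4 to 96.0);
- planned, supportive: 96/100 = 96.0% (90.1 to 98.9).

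The cost is one or two sentences and minor reprogramming, with no new data. The figure may be slightly less favourable. The report should state that, if stopping is unrelated to outcome, the version excluding departing successes is tilted down by about 0.1 to 0.8 points over 5 to 10 such stops and 2% to 10% failure per week.

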## **3.2 Secondary outcome variable**

### **3.2.1 Asthma Control Questionnaire-6**

The Asthma Control Questionnaire-6 (ACQ-6) is a shortened version of the ACQ that assesses asthma symptoms (nighttime waking, symptoms on waking, activity limitation, shortness of breath, wheezing, and short-acting  $\beta_2$  agonist use) omitting the forced expiratory volume in 1 second (FEV1) measurement from the original ACQ-7 score.

Patients are asked to recall how their asthma has been during the previous week by responding to 1 bronchodilator use question and 5 symptom questions. Questions are weighted equally and scored from 0 (totally controlled) to 6 (severely uncontrolled). The mean ACQ-6 score is the mean of the responses. The mean score will be missing if any symptom score is missing.

The questionnaire will be completed at the study center at Weeks -2, 0, 4, 8, 12, 16, 20 and IPD.

The outcome variable for ACQ-6 will be the change in mean score from baseline (Week 0) to each of the post-treatment periods. There will be no imputation for missing values.

Asthma control responder status will be evaluated as a supportive analysis. Patients will be categorized according to the following limits (Juniper et al 2005), at the end of treatment, where end of treatment is defined as week 20 (EOT visit):

- $ACQ-6 (EOT - baseline) \leq -0.5 \rightarrow$  Improvement
- $-0.5 < ACQ-6 (EOT - baseline) < 0.5 \rightarrow$  No change
- $ACQ-6 (EOT - baseline) \geq 0.5 \rightarrow$  Deterioration

An ACQ-6 responder will be defined as a patient who had improvement on ACQ-6, ie, an ACQ-6 responder variable takes value 1 if change from baseline to end of treatment in  $ACQ-6 \leq -0.5$  and 0 otherwise. Patients with missing or non-evaluable ACQ-6 data at end of treatment visit will be considered non-responders.

Additionally, patients will be categorized according to their ACQ-6 defined asthma control status at the end of treatment using the following score thresholds (Juniper et al 2006):

- $ACQ-6 (EOT) \leq 0.75 \rightarrow$  Well controlled
- $0.75 < ACQ-6(EOT) < 1.5 \rightarrow$  Partly controlled
- $ACQ-6 (EOT) \geq 1.5 \rightarrow$  not well controlled

### **3.2.2 Blood eosinophil levels**

Blood eosinophil counts levels will be evaluated at Screening (Week -2), Week 0 (baseline), EOT/IPD visit and Follow-up visit.

Blood samples for determination of eosinophil counts levels (hematology) will be taken at the time points detailed in the clinical study protocol (CSP), and will be assessed in a central laboratory. Eosinophils will be presented in both International System of Units (ie, SI) and conventional units (cells/ $\mu$ L) in summaries.

## **3.3 Safety variables**

Safety variables include AEs, hematology, clinical chemistry, urinalysis, vital signs, and electrocardiograms (ECGs).

All safety measurements will use all available data for analyses, including data from unscheduled visits and repeated measurements.

Change from baseline to each post-treatment time point where scheduled assessments were made will be calculated for relevant measurements. Adverse events will be summarized by means of descriptive statistics and qualitative summaries.

No safety data will be imputed. The handling of partial/missing dates is detailed in the programming specs.

### **3.3.1 Adverse events**

Adverse events (AEs) experienced by the patients will be collected throughout the entire study and will be coded using the latest version of the Medical Dictionary for Regulatory Activities (MedDRA) per the Data Management Plan.

Adverse event data will be categorized according to their onset date into the following study periods:

- AEs in the on-study period are defined as those with onset between day of the first dose of study treatment and scheduled follow-up visit, inclusive.
- AEs in the on-treatment period are defined as those with onset between day of first dose of study treatment and scheduled EOT for patients who complete study treatment or scheduled IPD visit for those patients who prematurely discontinue study treatment, inclusive. In the event that the EOT or IPD visit is beyond the protocol defined visit window, AEs with onset after the last dose of study treatment date+28 days+3 days (visit window) will be excluded from the on-treatment period and instead assigned to the post-treatment period.
- AEs in the post-treatment period are defined as those with onset after, but not including, the EOT visit (or the IPD visit) up to and including follow-up visit.

For instances where a patient attends the safety follow-up visit only, but does not attend an earlier IPD visit or EOT visit, AEs occurring on or after the day of the first dose of study treatment and on or before the last dose of study medication +28 days will be assigned to the on-treatment period, while AEs with onset date after this time will be assigned to the post-treatment period.

Adverse event on-study period is a combined period of on-treatment period and post-treatment period (when applicable).

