#### **4.1.2.1 Procedures for patients who experience an exacerbation during screening**

Patients who experience an asthma exacerbation during screening should be treated according to local medical practice.

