## **7.3 Recording of adverse events**

### **7.3.1 Time period for collection of adverse events**

Adverse events will be collected from the time the patient signs the informed consent, throughout the treatment period and including the follow-up period (through Week 28).

Serious adverse events will be recorded from the time of informed consent.

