### **7.3.3 Variables**

The following variables will be collect for each AE;

- AE (verbatim)
- The date when the AE started and stopped
- Maximum intensity of the AE
- Whether the AE is serious or not
- Investigator causality rating against the Investigational Product (yes or no)
- Action taken with regard to investigational product
- AE caused subject's withdrawal from study (yes or no)
- Outcome.

In addition, the following variables will be collected for SAEs:

- Date AE met criteria for serious AE
- Date Investigator became aware of serious AE
- AE is serious due to
- Date of hospitalization
- Date of discharge
- Probable cause of death
- Date of death
- Autopsy performed
- Causality assessment in relation to Study procedure(s)
- Description of AE

It is important to distinguish between serious and severe AEs. Severity is a measure of intensity whereas seriousness is defined by the criteria in Section 7.2. An AE of severe intensity need not necessarily be considered serious. For example, nausea that persists for several hours may be considered severe nausea, but not a SAE unless it meets the criteria shown in Section 7.2. On the other hand, a stroke that results in only a limited degree of disability may be considered a mild stroke but would be a SAE when it satisfies the criteria shown in Section 7.2.

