##### **4.2.10.2 Adverse events**

Adverse events will be summarized for the on-study, on-treatment, and post-treatment periods, as defined in Section 3.3.1. All AEs will be listed regardless of treatment period.

An overall summary table will be produced showing the number and percentage of patients with at least 1 AE in any of the following categories: AEs, deaths due to AE, serious AEs (SAEs), and AEs causing discontinuation of IP (DAEs). The total number of AEs in the different AE categories in terms of AE counts will also be presented (ie, accounting for multiple occurrences of the same event in a patient).

Adverse events, DAEs and SAEs will be summarized by SOC and PT assigned to the event by MedDRA. For each PT, the number and percentage of patients reporting at least 1 occurrence will be presented, ie, for a patient multiple occurrences of an AE will only be counted once. Serious AEs causing discontinuation of the study treatment and SAEs causing discontinuation from the study will also be summarized.

Adverse events and SAEs (by PT) will be summarized by Investigator's causality and maximum intensity. If a patient reports multiple occurrences of the same AE within the same reported period, the maximum intensity will be taken as the highest recorded maximum intensity (the order being mild, moderate, and severe). Deaths will also be summarized in separate tables.

A summary of the most common (ie, frequency of >5%) AEs will also be presented.

Adverse events of injection site reactions (high level term of administration and injection site) will be summarized by PT for the on-treatment period. In addition, if there are sufficient amount of hypersensitivity events (standardized MedDRA query of hypersensitivity), it will also be summarized by PT for the on-treatment period as well as the on-study period.

Separate listings of patients with AEs, SAEs, death due to AE, or discontinuations due to AEs will be presented.

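### SAP 3.3.1 assigns adverse events to periods by onset date only, so an event recorded with screening onset that turns serious, fatal or treatment-stopping after first dose is left out of the period-based safety tables

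*SAP*

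**What the plan says.** **Collection.** Protocol 7.3.1: "Adverse events will be collected from the time the patient signs the informed consent". Screening is planned to last 2 weeks, so AEs with screening onset will be in the database.

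**Fields.** Protocol 7.3.3 records one start and one stop date per AE, its maximum intensity, and the action taken with IP. For serious AEs it adds the date of death and, separately from the start date, "Date AE met criteria for serious AE".

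**Period assignment.** SAP 3.3.1 uses one criterion: "Adverse event data will be categorized according to their onset date into the following study periods". The widest period is defined thus: "AEs in the on-study period are defined as those with onset between day of the first dose of study treatment", ending at the scheduled follow-up visit. The SAP describes it as the on-treatment and post-treatment periods combined. No screening period is defined, and there is no rule for an event that starts before first dose and worsens afterwards.

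**Use in tables.** SAP 4.2.10.2: "Adverse events will be summarized for the on-study, on-treatment, and post-treatment periods, as defined in Section 3.3.1". The overall table has lines for AEs, deaths due to AE, serious AEs and AEs leading to IP discontinuation. The same section lists every AE whatever its period and plans separate death tables, for which it states no period rule.

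**The concern.** Protocol 7.3.3 allows the start of an event and the date it became serious to differ, but the SAP uses only the start. If the two dates fall on either side of the first injection, an outcome that occurred under treatment is tabulated nowhere by period.

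The effect runs in one direction. The rule can remove a post-dose serious, fatal or treatment-stopping outcome from a count and can never add one. Safety and tolerability is a stated objective, and readers take its counts and percentages from the tables. A patient who stopped IP for such an event could appear in disposition (SAP 4.2.1) as not having completed treatment yet be absent from the table of AEs leading to IP discontinuation, with nothing to explain the difference.

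The AE rule also differs from the laboratory rule. SAP 3.3.2 takes the maximum or minimum over the whole post-baseline period, so worsening of an abnormality present before dosing shows in the shift tables. SAP section 6 drops the physical-examination shift table because abnormal results go to the AE dataset, so more rests on the AE tables.

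**Working it through.** **Inputs.** First dose is study day 1, end of treatment day 141 and follow-up day 197 (SAP 2.2.2 visit-window tables). About 120 patients are treated (SAP 1.3).

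**Check of the plan's figure.** 100 completers / (1 − 0.17) = 120.5, and 20/120 = 16.7%. The planned 120 is reproduced, and it serves here only as the denominator.

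**The rule as written.** For onset day d in a patient who attends on schedule:
- on-study if 1 ≤ d ≤ 197
- on-treatment if 1 ≤ d ≤ 141
- post-treatment if 141 < d ≤ 197

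The key date below is the day the event became serious or fatal. In the last column, an event with no period by onset is assigned by its key date instead.

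| Onset day | Key date | SAP 3.3.1 | By key date when onset precedes first dose |
|---|---|---|---|
| −14 | 1 | none | on-study, on-treatment |
| −5 | 30 | none | on-study, on-treatment |
| −1 | 113 | none | on-study, on-treatment |
| −3 | 160 | none | on-study, post-treatment |
| 1 | 30 | on-study, on-treatment | unchanged |
| 30 | 30 | on-study, on-treatment | unchanged |

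Every event with onset before day 1 falls outside all periods, whatever happens later. Events with onset on or after day 1 are unaffected.

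**Size per omitted patient.** 1/120 = 0.83 percentage points. For scale, exact (Clopper-Pearson) 95% intervals are:
- 0/120: 0 to 1 − 0.025^(1/120) = 3.0%
- 1/120: 0.02% to 4.6%

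The documents give no number of affected patients. If 1 to 3 are assumed, the reduction is 1/120 = 0.8 to 3/120 = 2.5 points.

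**The case against.** Several points on the other side narrow the problem.

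- **A new record may be opened.** Protocol 7.1 counts deterioration of a pre-existing condition as an AE. A site could record the deterioration as a new event with post-dose onset, and the SAP would count it. This stands as a mitigation. However, no section requires a new record, and the maximum-intensity and date-of-seriousness fields fit a single continuing record equally well. Completeness then depends on site practice.
- **Nothing disappears.** A reader might infer that these events are lost. They are not: SAP 4.2.10.2 lists all AEs, with separate listings for serious AEs, deaths and discontinuations. In a study of about 120 patients with no hypothesis tests, a careful reader could find them there. The gap is in the tables.
- **Deaths.** A reader might infer that such a death is tabulated nowhere. That goes too far, because the separate death tables have no stated period restriction and could include it. The omission is shown only for the deaths-due-to-AE line of the period-based summary.
- **Screening exacerbations.** A tempting example is an exacerbation in screening that turns serious after dosing. Protocol 4.1.2.1 says only: "Patients who experience an asthma exacerbation during screening should be treated according to local medical practice". But Protocol 7.3.7 makes an exacerbation an AE only if it is serious, leads to study discontinuation, or is new to or inconsistent with the patient's asthma history. A typical non-serious one is not yet an AE in screening, and no section says its onset must be back-dated once it turns serious. Exclusion criteria 2, 7, 8 and 9 and the rescheduling rule in Protocol 6.6 further limit who would be dosed with an active problem. This route is ambiguous and does not establish the point.
- **Frequency.** Screening is 14/(14 + 197) = 6.6% of the days from consent to scheduled follow-up. A reader might take that as the share of AEs affected. It is a share of days. An affected AE must also persist past first dose and then become serious, fatal or treatment-stopping, and the documents give no rate for that.

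**Conclusion.** The gap is real but narrow. Under SAP 3.3.1 as written, an AE recorded with screening onset and kept on that record enters no period-based AE, serious AE, IP-discontinuation or deaths-due-to-AE count, even if the outcome that matters occurred after first dose. This follows from the period definitions and needs no assumption about rates. It does depend on the site continuing the original record, which the protocol neither requires nor rules out.

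Cases should be rare, and their number cannot be derived from the documents. Each one lowers a percentage by about 0.83 points if 120 patients are treated, always downward. The practical risk is a table reporting zero, or one too few, for a serious outcome that the listings contain. The documents do not support a claim of substantial undercounting. The point merits correction because the remedy is cheap and removes a one-directional error.

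**What to change.** Add to SAP 3.3.1, for patients in the full analysis set:

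*An AE with onset before the first dose is also counted in the on-study period, and in the on-treatment or post-treatment period as applicable, if it met a seriousness criterion or was fatal on or after the day of first dose, using the recorded date of seriousness or date of death. If the action taken with IP was discontinuation, it is counted as on-study and on-treatment. These cases are identified by a footnote and keep their recorded onset date in the listings.*

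The discontinuation clause uses no discontinuation date because Protocol 7.3.3 lists the action taken without one. None is needed: stopping IP necessarily follows first dose. Worsening in intensity alone is left out because only maximum intensity is recorded and it cannot be dated. The SAP should also state which period or population rule applies to the separate death tables.

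**Cost.** A short addition to the SAP before database lock, which Protocol 8.1 allows, and a little programming with fields already collected. Reported counts may be slightly higher.
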